4.1. Stratification and Covariates

There are no formal plans for analysis stratification or use of covariates.

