4. DATA ANALYSIS CONSIDERATIONS

Unless noted otherwise, the following statistical considerations will be applied:

- All analyses will be conducted based on Statistical Analysis System (SAS[®]) software version 9.4 or higher.
- Data for all sites/centers will be pooled for analysis.
- All data in the database except birth date will be presented in by-patient data listings.
- Listings will be sorted by cohort, patient identification number (concatenated site and patient number), and assessment date (and time, if available). If assessment date is missing, chronological visit will be used for sorting.
- Continuous data will be summarized by cohort (or last assigned dose level, as applicable) based on n, mean, median, standard deviation (SD), 25th percentile/first quartile (Q1), 75th percentile/third quartile (Q3), minimum value, and maximum value.
- Categorical data will be summarized by cohort using n and percentage based on the number of non-missing values.
 - The number of missing values will be presented as a separate category with no percentage, but only if one or more patients are missing data.
 - Counts of zero will be presented without percentages.
- Statistics will be presented in the summary tables based on the following:
 - Mean, Median, Q1, and Q3: one additional decimal place to that reported for Minimum and Maximum
 - SD: two additional decimal places than the Minimum and Maximum

- Percentages: reported to one decimal place
- P-values will be reported to four decimal places. If the value is below 0.0001 it will be noted as < 0.0001; if the value above 0.9999 it will be noted as > 0.9999.
- The number and percentage will be presented in the form of XX (XX%). Percentage values of less than 1% will be presented as XX (<1%).
- Statistical inference will be based on a 5% significance level (i.e., 95% confidence intervals [CIs] will be produced). CIs will be produced only in cases with sufficient sample size (i.e., n => 5).
- Change from baseline = value (post-baseline visit) – value (baseline or last visit prior to treatment).
- All data up to the time of study completion/withdrawal from the study will be included in the analysis, regardless of duration of treatment.
- Numbering for data displays will be based on the International Council for Harmonization E3.
- The protocol uses the terms cohort, treatment group, and treatment arm interchangeably. For consistency in this document, the term cohort will be used.

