5.7. Multiple Assessments and Visit Windows

If there are multiple assessments at a scheduled visit, then the last assessment will be used in the analysis.

Nominal visits (e.g., those identified by the study eCRF) will be the basis of summarization and statistical analysis; visit windows for each scheduled visit can be found in the Schedule of Activities from the protocol. Unscheduled data may be included in summaries of baseline and maximum/minimum change values; summaries of specific abnormalities any time post-baseline; and patient data listings.

Sponsor: Boston Pharmaceuticals, Inc.
Protocol Number: BOS-589-201
Version and Date: Version 1.2 12NOV2020

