5.8. Lost to Follow Up or Lapse of Adequate Assessments

A patient will be considered lost to follow-up if he or she repeatedly fails to return for scheduled visits and is unable to be contacted by the study site staff. Missing evaluations will not be imputed.

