6. STUDY PATIENT DATA

6.1. Analysis Sets

- The Screened Analysis Set will include all patients who have signed an informed consent document.
- The Intention-to-Treat (ITT) Analysis Set will include all randomized patients.
- The Per Protocol (PP) Analysis Set will include all patients in the ITT Analysis Set who received at least 1 dose of study drug and did not have any major protocol deviations.
- The Safety (SAF) Analysis Set will include all patients who received at least 1 dose of study drug.

Sponsor: Boston Pharmaceuticals, Inc.
Protocol Number: BOS-589-201
Version and Date: Version 1.2 12NOV2020

All safety analyses will be performed in the SAF Analysis Set by the actual cohorts. All efficacy analyses will be performed in the ITT and PP Analysis Sets by the randomized cohorts. Summaries of the Screened Analysis Set will be performed by the randomized cohorts.

The criteria for inclusion in the PP Analysis Set will be finalized and documented before database is locked and study unblinding. Additional information on inclusion into this population can be found in Section 6.3.

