7. EFFICACY

Efficacy analyses will be conducted using the ITT and PP Analysis Sets.

All available efficacy data will be provided in by-patient data listings on all ITT patients.

The efficacy objectives of the study are to evaluate the effect of BOS-589, relative to Placebo after 4 weeks of therapy, on pain, defecation, and key IBS-D related signs and symptoms.

During the 4 weeks of the double-blind treatment phase, patients will be required to access their electronic diary every day, preferably at the same time each day, to record IBS-D symptom data and information related to their bowel function and rescue medication use.

For all efficacy endpoints, the Day 29 visit change from baseline is the main timepoint of interest. However, unless stated otherwise, data will be presented for each planned visit (Baseline/Day 1, Day 8, Day 15, Day 22, Day 29, and Day 43).

For efficacy endpoints collected daily, the baseline score will be the average of non-missing scores reported for the last 7 days prior to the date where eligibility and run-in criteria pertaining to IBS-D symptom and bowel function have been met. The Day 29 visit score will be the average of non-missing scores reported during the 7 days prior to the Day 29 visit. The Day 8 visit, Day 15 visit, Day 22 visit, and Day 43 visit scores are calculated in a similar manner. If there are missing daily scores on any day, the visit score will be averaged from all the non-missing values during the 7 days prior to the visit. No imputation of the missing values will be made. For the Day 29 calculation only, a window of ± 14 days relative to actual calculated day 29 from dosing will be applied such that any Day 29 visit occurring outside that window will be excluded.

Sponsor: Boston Pharmaceuticals, Inc.
Protocol Number: BOS-589-201
Version and Date: Version 1.2 12NOV2020

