7.1. Primary Efficacy Endpoint and Analyses

7.1.1. Worst Abdominal Pain

The primary efficacy endpoint will be defined as a change in the 24-hour WAP score at the Day 29 visit compared to baseline (averaged over the week prior to the visit). The 24-hour WAP score will be a patient-reported score of their WAP in the past 24 hours on a 0 to 10 scale, where 0 corresponds to no pain and 10 corresponds to worst imaginable pain. Patients will be asked to rate their WAP in the past 24 hours every day for the entire Run-in period and the 4-week double-blind treatment period.

This is a proof-of-principle study in which a hierarchical hypothesis test will be employed for the primary efficacy endpoint. The mean change in 24-hour WAP at the Day 29 visit from baseline (averaged over the week prior to the visit) will be measured as a continuous variable and compared between cohorts in the following testing order using a t-test of equal variances and a two-tailed alpha of 0.05:

Hypothesis 1:

Active Treatment (Cohort 1 + Cohort 2) versus Placebo (Cohort 3);

$$H_0: \mu_1 = \mu_2$$

$$H_1: \mu_1 \neq \mu_2$$

The null hypothesis will be that there is no difference in the mean change in 24-hour WAP score at the Day 29 visit from Baseline (averaged over the week prior to the visit) between active treatment and Placebo. The alternative hypothesis will be that there is a difference in the mean change in 24-hour WAP score at the Day 29 visit from Baseline (averaged over the week prior to the visit) between active treatment and Placebo. The test statistic is:

$$t = \frac{\bar{x}_1 - \bar{x}_2}{\sqrt{s^2(\frac{1}{n_1} + \frac{1}{n_2})}}$$

\bar{x}_1 and \bar{x}_2 are the sample means of change at the Day 29 visit from Baseline in 24-hour WAP score (averaged over the week prior to the visit), s^2 is the pooled sample variance assuming equal variance, n_1 and n_2 are the sample sizes, and the degree of freedom is $n_1 + n_2 - 2$.

If statistically significant at $P < 0.05$, then proceed to Hypothesis 2.

Hypothesis 2:

Cohort 1 (High Dose) versus Cohort 3 (Placebo);

Sponsor: Boston Pharmaceuticals, Inc.
Protocol Number: BOS-589-201
Version and Date: Version 1.2 12NOV2020

If statistically significant at $P < 0.05$, then proceed to Hypothesis 3.

Hypothesis 3:

Cohort 2 (Low Dose) versus Cohort 3 (Placebo);

If statistically significant at $P < 0.05$ then, proceed to Hypothesis 4.

Hypothesis 4:

Cohort 1 (High Dose) versus Cohort 2 (Low Dose).

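### The primary pain test does not adjust for baseline pain score, and no sensitivity analysis covers randomized patients without an in-window Day 29 score

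*SAP*

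**What the plan says.** Protocol 9.4.1.1 and SAP 7.1.1 agree on the primary analysis. Change in weekly-average WAP at Day 29 is "compared between cohorts in the following testing order using a t-test of equal variances and a two-tailed alpha of 0.05", with a pooled variance and n1 + n2 − 2 degrees of freedom. SAP 4.1 states: "There are no formal plans for analysis stratification or use of covariates". Baseline WAP is therefore used only by subtraction.

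On missing data, Protocol 9.4.1.4 makes sensitivity analyses optional and leaves the methods to the SAP. The SAP then says:

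- Section 6.1: "The Intention-to-Treat (ITT) Analysis Set will include all randomized patients".
- Section 7: the visit score averages whatever daily scores exist in the 7 days before the visit; "No imputation of the missing values will be made"; a ±14-day window applies to Day 29, and "any Day 29 visit occurring outside that window will be excluded".
- Section 5.8: "Missing evaluations will not be imputed".
- Section 5.10 refers to Section 7 for efficacy imputations, but Section 7 makes none.
- Section 7.1.1: the one WAP analysis labelled as a sensitivity analysis repeats the test in patients with screening fecal calprotectin under 50 mcg/g.

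Other provisions limit the loss. Protocol 7.1 keeps patients in the study after they stop drug. SAP 4 says "All data up to the time of study completion/withdrawal from the study will be included in the analysis, regardless of duration of treatment". In the Schedule of Activities, Early Termination shares Visit 7 with Day 29, and SAP 5.7 says "Nominal visits (e.g., those identified by the study eCRF) will be the basis of summarization and statistical analysis".

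**The concern.** There are two separate gaps in the same primary analysis.

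First, every eligible patient has a run-in WAP average (Protocol 5.1 requires 3.0 to 8.0). A plain change score forces the slope of Day 29 on baseline to be 1. If the true slope is lower, change is correlated with baseline, and the t-test leaves that explainable variation in its error term. It also gives no protection against chance baseline imbalance. What is lost is precision, not type I error control. It matters somewhat because Hypothesis 1 gates every later test and the planned power is only approximately 80%.

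Second, the ITT set is all randomized patients, but the t-test can use only those with an in-window Day 29 score. The per-protocol repeat removes more patients and restores none, and the calprotectin analysis is a subgroup analysis. Nothing planned would show whether a borderline result depends on the patients who are absent.

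**Working it through.** **Inputs from the plan** (SAP 3.4; Protocol 9.2): difference 1.6, SD 3, two-sided alpha 0.05, 120 patients after allowance, 132 randomized 1:1:1. Hypothesis 1 compares pooled active with placebo, so 80 v 40 evaluable or 88 v 44 randomized.

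**Step 1. Reproduce the stated power.** Noncentral t with noncentrality 1.6 / (3 × √(1/n1 + 1/n2)):

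- 80 v 40: 78.0% (78.6% by the normal formula), consistent with the SAP's approximate 80%
- 88 v 44: 81.8%
- one dose v placebo, 40 v 40: 65.4%

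**Step 2. Gain from baseline adjustment.** Let b be the slope of Day 29 WAP on baseline and SDb the baseline SD. Baseline explains SDb² × (1 − b)² of the variance of change, so the fraction removed is SDb² × (1 − b)² / 9. The documents give neither b nor SDb. Assumed ranges are b = 0.3 to 0.7 and SDb = 1.0 to 1.44; the upper value is a uniform spread over the 3 to 8 entry range, 5/√12 = 1.44.

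| SDb | b | Variance removed | Power, 80 v 40 |
|---|---|---|---|
| 1.0 | 0.7 | 1.0% | 78.4% |
| 1.0 | 0.5 | 2.8% | 79.1% |
| 1.0 | 0.3 | 5.4% | 80.2% |
| 1.2 | 0.7 | 1.4% | 78.6% |
| 1.2 | 0.5 | 4.0% | 79.6% |
| 1.2 | 0.3 | 7.8% | 81.2% |
| 1.44 | 0.7 | 2.1% | 78.8% |
| 1.44 | 0.5 | 5.8% | 80.3% |
| 1.44 | 0.3 | 11.3% | 82.7% |

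The range, 1.0% to 11.3%, is worth about 1 to 14 of 120 patients (0.010 × 120 = 1.2; 0.113 × 120 = 13.6). At 88 v 44, power becomes 82.2% to 86.1%; at 40 v 40, 65.8% to 70.6%. Simulating the three-arm ANCOVA contrast (20,000 trials, 40 per arm) gave power of 78.2% to 82.5% and type I error of 4.8% to 4.9%.

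If a correlation of 0.2 to 0.5 between change and baseline is assumed directly, the normal formula gives about 80% to 89%. The upper end is hard to reach here. A correlation of 0.5 needs SDb × (1 − b) = 0.5 × 3 = 1.5, and with SDb = 1.44 that requires a slope just below zero. The table is the more cautious range.

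**Step 3. Who leaves the primary test.** The ±14-day window runs from about Day 15 to Day 43. A patient who stops drug but stays in follow-up can still supply a Day 29 score. A patient who leaves the study from about Day 15 has an Early Termination visit recorded as Visit 7 and can reasonably be read as retained. However, SAP 9 equates Day 29 with early termination for safety only; Section 7 has no matching statement for efficacy. Certain loss is confined to patients with no in-window score.

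**Step 4. How much the missing patients could matter.** No dropout rate is given, and the 12-patient allowance also covers a higher placebo rate. As an illustration, take all 12 as missing: 80 of 88 active and 40 of 44 placebo observed.

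- SE = 3 × √(1/80 + 1/40) = 0.581
- smallest significant difference = 1.980 × 0.581 = 1.150
- if the 8 missing active patients did worse than the observed active patients by delta, and missing placebo patients resembled observed ones, the difference falls by delta × 8/88
- with the SE held fixed, significance is lost at delta = (observed difference − 1.150) / (8/88)

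| Observed difference | Delta at which significance is lost |
|---|---|
| 1.6 | 4.9 |
| 1.4 | 2.7 |
| 1.2 | 0.5 |

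**The case against.** The strongest reply is that the pre-specified t-test is valid, already uses baseline through the change score, and is the test the sample size was planned for. At 88 v 44 it has 81.8% power without adjustment. The gain rests on a slope and SD that no document supplies, and at the low end it is 0.4 percentage points. For a phase 2a proof-of-principle study that may not justify a protocol amendment. All of this stands, and it is why the point is one of precision rather than validity. It does not make the adjustment worthless: the data are already collected, and the supportive version needs no amendment.

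On missing data, the loss is limited and will be visible. Discontinuations with reasons are summarized by cohort, efficacy data are listed for all ITT patients, and the protocol's wording on sensitivity analyses is permissive, so no commitment is broken. Taking all 12 patients as missing may be pessimistic. With half that loss (84 v 42 observed, 4 active missing) the critical difference is 1.12, and the deltas rise to about 10.5, 6.1 and 1.7 for observed differences of 1.6, 1.4 and 1.2. This also stands: the planned effect is robust. But counts and listings do not show whether a narrow result would survive, and choosing that analysis after unblinding would carry little weight.

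It is also fair that these are two issues. ANCOVA does nothing for patients without a Day 29 score; they need the separate sensitivity analysis.

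**Conclusion.** Both parts hold, and both are modest. Under the assumed ranges in the working, not using baseline WAP costs 0.4 to 4.7 percentage points of power for Hypothesis 1 at 80 v 40, with no effect on validity. The size of the gain cannot be fixed from the documents.

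The bias from patients without an in-window score is unknown. It is zero if the proportion lost and the gap between missing and observed patients are the same in both groups. On the illustrative 12 missing, a 1.6-point result would survive any plausible penalty, while one near 1.2 might not, and the SAP has no analysis that would tell the two apart. The plan should be changed, but the trial does not fail without the change.

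**What to change.** In SAP 4.1, 4.3 and 7.1.1, analyse Day 29 WAP change by ANCOVA with cohort (three levels) and baseline WAP, or by a repeated-measures model on Days 8, 15, 22 and 29 with baseline WAP. Test Hypotheses 1 to 4 as Day 29 contrasts in the existing order at 0.05, with Hypothesis 1 as the mean of Cohorts 1 and 2 minus Cohort 3.

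Add one pre-specified missing-data sensitivity analysis over all randomized patients, for example a delta adjustment from 0 to 5 points for missing active patients, reporting the delta at which significance is lost.

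Two wording changes belong with this: say whether an early-termination Visit 7 inside the window counts as Day 29 for efficacy, and correct the Section 5.10 pointer to imputations that Section 7 does not contain.

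Optionally, add a Welch test as a supportive check, because Hypothesis 1 is a 2:1 comparison. With assumed active/placebo SDs of 2.5/3.5 the pooled test's simulated type I error is 7.8%, and with 3.5/2.5 it is 3.0%; Welch stays at 4.9% to 5.0%. No document supports either direction.

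The cost is SAP text and some programming, with no new data or patients. Replacing the primary test needs the protocol amendment required by Protocol 9.4, and Protocol 10.1.1 requires regulatory approval first for amendments that change the study design. If that is not wanted, name the adjusted model as supportive and add the sensitivity analysis in the SAP alone, before unblinding.

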4.2. Evaluation of Subgroups

No subgroup analyses are powered for the study. However, analyses for the primary and secondary endpoints will be analyzed by sex, and fecal calprotectin < 50 mcg/g at screening, and possibly other subgroups based on emerging data.

4.3. Multiple Comparisons and Multiplicity

A hierarchical hypothesis test will be employed for the primary efficacy endpoint, in the following pre-defined testing order using a t-test of equal variances and a two-tailed alpha of 0.05:

Hypothesis 1:

Active Treatment (Cohort 1 + Cohort 2) versus Placebo (Cohort 3);

If statistically significant at P < 0.05, then proceed to Hypothesis 2.

Hypothesis 2:

Cohort 1 (High Dose) versus Cohort 3 (Placebo);

If statistically significant at P < 0.05, then proceed to Hypothesis 3.

Sponsor: Boston Pharmaceuticals, Inc.
Protocol Number: BOS-589-201
Version and Date: Version 1.2 12NOV2020

Hypothesis 3:

Cohort 2 (Low Dose) versus Cohort 3 (Placebo);

If statistically significant at $P < 0.05$ then, proceed to Hypothesis 4.

Hypothesis 4:

Cohort 1 (High Dose) versus Cohort 2 (Low Dose).

P-values presented in the analyses of secondary endpoints are displayed for descriptive purposes only and are not adjusted for multiplicity.

5. GENERAL DATA HANDLING CONVENTIONS

5.1. Assigned and Actual Treatment

Patients will be randomized via IWRS in a 1:1:1 ratio to receive BOS-589 200 mg, BOS-589 50 mg, or Placebo. Patients will be assigned to the cohorts using a permuted block randomization stratified by site (44 patients per group).

The assigned treatment is determined by a randomization schedule. The randomization schedule will be generated and will be transferred to the IWRS team for loading into the system. The actual treatment given to individual patient is the actual treatment.

All safety analyses will be based on the actual treatment. Study patient data and all efficacy analyses will be based on the assigned treatment unless specified otherwise.

5.2. Reference Dates

Reference dates are defined as follows:

- Screening date is defined as the electronic case report form (eCRF) provided visit date on which a patient was screened for trial entry.
- Informed consent date is defined as the eCRF provided date of informed consent from the informed consent page.
- Run-in period start date is defined as earliest date of eCRF provided visit date from the Run-in period page.
- Run-in period end date is defined as eCRF provided date of randomization -1 from the randomization page.
- Treatment start date is defined as the date of first dose of any study drug.
- Treatment end date is defined as the date of last dose of any study drug.
- Age will come directly from the eCRF which is integrated from IWRS based on the informed consent date.

Sponsor: Boston Pharmaceuticals, Inc.
Protocol Number: BOS-589-201
Version and Date: Version 1.2 12NOV2020

- Safety data, such as AEs and laboratory assessments, will use the treatment start date as a reference date.
- Efficacy data will use the treatment start date as a reference date.
- Study day will be based on treatment start date as a reference date. Study Day 1 will be the day patients start the first dose of study drug.

5.3. Study Day and Duration Variables

Reference date calculations will generally be defined as the following, assuming non-missing dates:

- date of interest – reference date + 1 when the date of interest \geq reference date;
- otherwise, date of interest – reference date.

If either date is missing, reference date calculations will not be performed. Date imputation will be performed as identified in Section 5.6.

Study day will either have a negative value if collected before dosing or a positive value if collected on or after the day of drug dosing; there will be no study day zero.

Duration of time is dependent on reference dates and will be calculated in a manner similar to that of the reference date calculation. Duration on study is defined as the end of study date – informed consent date + 1. Duration of treatment is defined as treatment end date – treatment start date + 1, where treatment end date is the date of last dose of study drug. Patients still receiving ongoing treatment or participating in study follow up at the time of analysis will use imputed treatment end and end of study dates as described in Section 5.7.

Durations reported in days will be calculated as measure date – reference date + 1. When reporting in months the result will be divided by 30.4375; for reporting in weeks it will be divided by 7; and for reporting in years it will be divided by 365.25.

5.4. Study Time Periods

Where applicable, data reporting will be classified by the following study periods for analysis:

- Pre-treatment is defined as the period prior to a patient's treatment start date.
- On-treatment is defined as the period between a patient's treatment start date and treatment end date. Treatment end date is defined as the date of last dose of study drug.
- Post-treatment is defined as the period of time following the on-treatment period.

5.5. Baseline and Post-Baseline Changes

Unless stated otherwise, baseline and post-baseline change values will be based on the following:

Sponsor: Boston Pharmaceuticals, Inc.
Protocol Number: BOS-589-201
Version and Date: Version 1.2 12NOV2020

- Baseline will be based on the last non-missing value (including unscheduled assessments) collected prior to or on the treatment start date/time for measures collected prior to the treatment.
- Post-baseline values will be those collected after the date/time of first dose of study drug.
- Change from baseline is defined as: value – baseline value.
- Percentage change from baseline is defined as: $(\text{value} - \text{baseline value}) / \text{baseline value} \times 100\%$.
- Maximum change will be based on the change from baseline value to the maximum value for all post-baseline assessments collected during the on-treatment period, scheduled or unscheduled, using the formulas above.
- Minimum change will be based on the change from baseline value to the minimum value for all post-baseline assessments collected during the on-treatment period, scheduled or unscheduled, using the formulas above.

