1.3 Schedule of Activities

Table 1. Schedule of Activities

Procedures	Pre-treatment		Treatment					Follow-up	
	Screening Days -36 to -1, Study Visit 1	Run-in Period ^a Days -15 to -1, Study Visit 2	Baseline Day 1, Study Visit 3	Day 8 (± 1 day) Study Visit 4	Day 15 (± 1 day) Study Visit 5	Day 22 (± 1 day) Study Visit 6	Day 29 (± 1 day) End of Treatment ^b /Early Termination ^b Study Visit 7	Day 43 (± 3 days) End of Study Study Visit 8	
Informed consent	X								
Demographics	X								
Medical and surgical history	X								
Rome IV assessment	X								
Concomitant medication review	X	X	X	X	X	X	X	X	
Adverse event review and evaluation		X	----- continuous -----					X	
Physical examination ^c	X		X				X		
Height, weight, and body mass index	X ^d		X		X		X	X	
Vital signs	X		X	X	X	X	X	X	
12-lead electrocardiogram	X						X		
Clinical safety laboratory tests ^e	X		X		X		X	X	
HIV, HCV/HBV testing	X								
Urine pregnancy test	X		X				X	X	
C-reactive protein and erythrocyte sedimentation rate tests	X		X		X		X	X	
Biomarker sample collection			X		X		X	X	
Pharmacokinetic sample collection ^f			X	X	X	X			
Worst abdominal pain	X	X ^g	X	----- ^h -----					X ^h
Bristol Stool Form Scale	X	X ^g	X	----- ^h -----					X ^h

Procedures	Pre-treatment		Treatment					Follow-up
	Screening Days -36 to -1, Study Visit 1	Run-in Period ^a Days -15 to -1, Study Visit 2	Baseline Day 1, Study Visit 3	Day 8 (± 1 day) Study Visit 4	Day 15 (± 1 day) Study Visit 5	Day 22 (± 1 day) Study Visit 6	Day 29 (± 1 day) End of Treatment ^b /Early Termination ^b Study Visit 7	
Spontaneous bowel movements (total number of stools)		X ^g	X ^h	----- ^h	----- ^h	----- ^h	----- ^h	X ^h
IBS-GS		X ^g	X ^h	----- ^h	----- ^h	----- ^h	----- ^h	X ^h
Rescue medications		X ^g	X ^h	----- ^h	----- ^h	----- ^h	----- ^h	X ^h
IBS-SS			X				X	X
Eligibility review	X		X					
Randomization			X					
Administration of investigational product			Day 1	-----	-----	-----	-----	Day 28

HBV = hepatitis B virus; HCV = hepatitis C virus; HIV = human immunodeficiency virus; IBS-GS = Irritable Bowel Syndrome Global Scale;
 IBS-SS = Irritable Bowel Syndrome Severity Score.

^a Run-in may be extended by up to one week in accordance with the investigators judgement. The full 5 week (Days -36 to -1) may be used to randomize eligible patients. However, efforts should be made to randomize eligible patients within 1 to 3 days after completing run-in period.

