4.1.3 Replacement of Patients

Patients who sign the ICF and are randomized but do not receive the investigational product may be replaced. Once randomized, patients who have received at least 1 dose of investigational product and are withdrawn from therapy before completing 28 days of dosing or are discontinued from the study for any reason will not be replaced.

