9.2. Clinical Laboratory Evaluations

Laboratory tests identified in Appendix 1 in the protocol will be performed at times defined in the Schedule of Activities, Section 1.3 of the protocol. Clinical chemistry, hematology, and coagulation parameters will be reported based on the International System of Units (SI). All abnormal laboratory results will be evaluated by the Investigator as either clinically significant or not clinically significant.

Observed values and changes from baseline for hematology, clinical chemistry, urinalysis, and inflammatory biomarker laboratory evaluations will be summarized by cohort at each scheduled visit (Baseline/Day 1, Day 15, Day 29/Early Termination, and Day 43/End of Study) and most extreme change.

Box plots will be produced by visit and treatment for the recorded values of Erythrocyte Sedimentation Rate, C-reactive Protein, and Fecal Calprotectin. As well, line plots of the mean change from baseline of these three tests at each visit will be produced by treatment.

The number and percentage of patients experiencing treatment-emergent graded toxicities will be summarized by cohort and severity grade per the National Cancer Institute Common Terminology Criteria for Adverse Events (CTCAE) version 4.0.3. For each parameter, a patient will only be counted once using the worst-case value among all post-baseline timepoints. Laboratory toxicity will be summarized by incidence of CTCAE grade 3 and CTCAE grade 4 values for measures with a corresponding CTCAE grade. For measures without a corresponding CTCAE grade, incidence of 2.5 to < 5.0 X upper or lower limit of normal and ≥ 5.0 X upper or lower limit of normal cohort by cohort. Patients with missing values post-baseline will be excluded from the summary. The denominator for percentages will be the number of patients with at least one post-baseline assessment for the laboratory parameter being displayed. Separate summary counts will be prepared for parameters with bi-directional toxicity grading with “high/hyper” conditions depending on the maximum post-baseline value and the “low/hypo” conditions depending on the minimum post-baseline value.

All laboratory parameters will be provided in patient data listings for all enrolled patients.

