9.3.3. Vital Signs

Vital signs include: pulse rate (beats/min), respiratory rate (breaths/min); temperature (degrees Celsius [°C]); systolic and diastolic blood pressure (millimeters of mercury [mmHg]); height, weight (kg), and BMI (derived).

Observed values and changes from baseline for vital signs will be summarized at by cohort and overall for each scheduled visit (Baseline/Day 1, Day 8, Day 15, Day 22, Day 29, and Day 43) and most extreme change.

Summaries of pulse rate, temperature, systolic blood pressure, and diastolic blood pressure will be based on markedly abnormal criteria defined below:

Vital Sign	Markedly Abnormal Criteria
Pulse rate (beats/min)	< 60 beats/min ≥ 100 beats/min
Temperature (°C)	≤ 35 °C ≥ 38 °C
Systolic blood pressure (mmHg)	120-139 mmHg, inclusive (CTCAE grade 1) 140–159 mmHg, inclusive (CTCAE grade 2) ≥ 160 mmHg (CTCAE Grade 3)
Diastolic blood pressure (mmHg)	80–89 mmHg, inclusive (CTCAE grade 1) 90–99 mmHg, inclusive (CTCAE grade 2) ≥ 100 mmHg (CTCAE grade 3)

Incidence of post-baseline markedly abnormal worst-case values will be presented. For pulse rate and temperature, both high and low values will be presented separately such that patients can be counted in both categories.

All vital signs data will be presented in patient data listings for all enrolled patients. Markedly abnormal vital sign values will be flagged as such in the vital signs listing.

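### As worded, the SAP's maximum and minimum change rule ends at the last dose, so the most-extreme-change rows for labs and vital signs leave out end-of-treatment tests taken on Day 29 or 30

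*SAP*

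**What the plan says.** SAP 5.5 bases both maximum and minimum change on values "for all post-baseline assessments collected during the on-treatment period", whether scheduled or not. It applies unless something else is stated.

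SAP 5.4 sets the period: "On-treatment is defined as the period between a patient's treatment start date and treatment end date". It then adds: "Treatment end date is defined as the date of last dose of study drug". No days are added after the last dose.

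SAP 9.2 lists the lab summary visits and ends the list with "Day 29/Early Termination, and Day 43/End of Study) and most extreme change". SAP 9.3.3 does the same for vital signs: "and most extreme change". Neither section gives that row a period of its own, and the SAP does not define it by that name.

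In Protocol 1.3 (Table 1), the row "Administration of investigational product" runs from Day 1 to Day 28. Protocol 4.1.3 agrees, speaking of patients "withdrawn from therapy before completing 28 days of dosing". The End of Treatment/Early Termination visit is Day 29 (±1 day), and a footnote places Early Termination procedures close to the stopping of dosing.

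**The concern.** A row showing each patient's most extreme change should contain the end-of-treatment sample. As worded, for a patient on schedule, it does not. Safety and tolerability over 4 weeks is a primary objective, and the earlier repeat dosing described in the protocol lasted 14 days. Weeks 3 and 4 are therefore the exposure this trial adds, and the lab row would contain no scheduled draw from them. Tests taken when a patient stops drug early would also be missing whenever they fall after the last-dose date.

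The rule also treats similar patients differently. Two patients with the same dosing and the same results can have different entries in the row because one came in on Day 28 and the other on Day 29.

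**Working it through.** The documents give no figure on this point, so the check is a classification of visits. An assessment counts if it follows the first dose and falls on or before the last-dose date.

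Inputs: planned last dose Day 28 (Protocol 1.3, 4.1.3); post-baseline labs at Days 15, 29 and 43 (SAP 9.2); post-baseline vital signs at Days 8, 15, 22, 29 and 43 (SAP 9.3.3); windows of ±1 day through Day 29 and ±3 days at Day 43 (Protocol 1.3).

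**Nominal visit days**

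| Last dose | Labs counted | Vital signs counted |
|---|---|---|
| Day 28 (planned) | Day 15: 1 of 3 | Days 8, 15, 22: 3 of 5 |
| Day 29 (assumed) | Days 15, 29: 2 of 3 | Days 8, 15, 22, 29: 4 of 5 |
| Day 30 (assumed) | Days 15, 29: 2 of 3 | Days 8, 15, 22, 29: 4 of 5 |

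**End-of-treatment window.** It spans Days 28, 29 and 30. With a last dose on Day 28, only Day 28 counts (1 of 3 permitted days). With a last dose on Day 29, 2 of 3 count; on Day 30, 3 of 3. Day 43 (window Days 40 to 46) never counts.

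**Consequence for labs.** With Day 15 as the only scheduled value and no unscheduled on-treatment draw, the maximum and minimum change both equal the Day 15 change, so the row repeats the Day 15 row. A patient who stops before Day 15 has no scheduled lab in it unless the Early Termination draw falls on the last-dose date.

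**Other periods in the same SAP**

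- Section 4: by default, data up to study completion or withdrawal are analysed whatever the treatment duration.
- Section 6.7: for rescue medication, the treatment period runs through Day 29.
- Section 9.2: lab toxicity takes the worst value over all post-baseline timepoints.
- Section 9.3.3: markedly abnormal vital signs use post-baseline worst-case values.
- Appendix 1: an adverse event with a known start date is treatment-emergent if it begins before end of treatment plus 15 days.

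Among these, only the maximum and minimum change rule stops at the last dose, and no reason is given.

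**The case against.** The strongest reply is that the link is inferred. Sections 9.2 and 9.3.3 name the row directly after visit lists that include Days 29 and 43, and Section 5.5 yields where something else is stated. The mock shells, which might settle it, are a separate document. Protocol 8.1 runs the Treatment Phase to the Day 29 visit, and SAP 9 labels Day 29 as end of treatment. This stands in part: the programmers may intend to include Day 29. But no other definition of the row exists in the SAP. If Section 5.5 does not govern it, the row is undefined, and clarification is needed either way.

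Second, the Day 29 values are not lost. They appear in the by-visit summaries (which report minimum and maximum), the CTCAE table, the markedly abnormal vital-sign table and the listings. Clinically relevant lab changes are also recorded as adverse events. This stands fully and limits the point to one descriptive row. The CTCAE table is only a partial substitute: it shows grades 3 and 4, or at least 2.5 times a normal limit where no grade exists, so smaller late shifts do not appear there.

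Third, an on-treatment limit is a coherent choice, since Day 43 is about two weeks off drug. This also stands: the documents do not require Day 43 in the row.

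**Conclusion.** The point holds as a wording defect in the SAP. It matters for how one safety row reads, not for the trial's conclusions. On the planned schedule the row uses 1 of 3 scheduled post-baseline labs and 3 of 5 vital-sign visits. This assumes a last dose on Day 28, an end-of-treatment visit on Day 29 or 30, and that the row means the maximum and minimum change of SAP 5.5.

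A reader might infer more than the documents support:

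- That the lab row rests on Day 15 alone and hides anything later. Unscheduled on-treatment values count (SAP 5.5, 5.7), and Protocol 8.4.5 calls for repeat testing of clinically significant abnormal labs.
- That blood pressure is blind after Day 15. Day 22 vital signs are included.
- That Day 29 is the only scheduled lab after full exposure. Day 43 is also scheduled; Day 29 is the one timed to the end of dosing.
- That a late safety signal would be missing from the report. The other outputs retain it.

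**What to change.** In SAP 5.5, say that most extreme change means the maximum and minimum change, and that for this purpose the period runs from first dose through the Day 29/Early Termination visit inclusive. That matches the treatment period in SAP 6.7 and removes the dependence on visit timing. Scheduled coverage rises to 2 of 3 for labs and 4 of 5 for vital signs.

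Using all post-baseline values, as SAP 9.2 and 9.3.3 do for their worst-case tables, is an acceptable alternative (3 of 3 and 5 of 5), provided the row is labelled as including off-drug Day 43 values.

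The cost is one phrase in the SAP and one period condition in the code. No new data are needed, and the primary efficacy test is unaffected.
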